7.2 Hormonal Therapy

As patients are required to have ER positive disease, all patients should be treated with anti-endocrine therapy per current guidelines. Treatment should be given at a minimum of 5 years post-surgery. The choice of anti-endocrine agent is at the discretion of the patient's medical oncologist, and dose and schedule should be consistent with the instructions in the drug package inserts. Hormone therapy cannot be initiated until after surgery. While patients should be strongly encouraged to complete a minimum of 5 years of anti-endocrine therapy, failure to do so for whatever reason will not result in a protocol deviation or be the cause of study withdrawal.

7.3 Trastuzumab

Trastuzumab or other anti-HER2 agents are permitted at the discretions of the patient's medical oncologist for patients whose tumors are HER2 positive. The dose and schedule of these agents should be per standard treatment protocol, but cannot be given until after surgery.

8.0 Surgery and Post-Operative Treatment

8.1 Breast conserving surgery

Breast conserving surgery (lumpectomy) and sentinel node biopsy will occur no sooner than 5 weeks following completion of RT, but should occur no later than 8 weeks. In patients with rectal cancer, this interval has been shown to produce optimal response to pre-operative radiation while maintaining low rates of post-operative complications (101). Surgical techniques such as needle localization will be performed at the discretion of the treating surgeon and in concordance with current standard of care. Oncoplastic procedures are discouraged, but will not be counted as a protocol violation or removal from the study.

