We anticipate that the rate of post-operative complications on this study will be more favorable than those reported by Horton et.al. On this study, the radiation dose and fractionation schedule will be much different than that used by Horton et.al. This regimen has been shown to be safe and effective in a recent phase III study in the post-operative setting. (95). Fractionating the dose allows normal tissues time to repair sublethal radiation injury. This would likely result in a lower rate of post-operative complications.

On the other hand, there are factors on this trial that may result in a higher rate of post-operative complications than anticipated. On this study, the interval between radiation and surgery is longer on this study than that reported on the Horton study (surgery within 10 days of radiation versus at least 35 days after radiation). This longer interval was selected based on recent data in the literature for pre-operative treatment for rectal cancer. In this disease site, waiting longer for surgery allows for improved tumor regression, improving the rate of margin negative resection, and allowing for a smaller resection. In the case of rectal cancer, this translates to sphincter preservation but may translate to an improved cosmetic result in the case of breast conserving surgery. These benefits have also translated to an improvement in disease-free survival for patients with rectal cancer (101). However, the longer interval from radiation to surgery may also lead to a slight, but tolerable increase in post-operative complications. It is anticipated that the reasons for a lower post-operative complication rate will dominate on this study. But given the potential for a higher rate than expected, the rate of the most common complication reported on the Horton study will be used as the historical control.

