9.0 Pathologic Evaluation and Genetic Evaluation of Tissue Specimens

9.1 Pathological Evaluation and Immune Biomarkers

- 9.1.1 The surgical specimens will be subject to routine pathological analysis. Remaining tissue from the pre-treatment biopsy, as well as any residual tumor tissue post-RT, will be stored in accordance with MCW department of Pathology guidelines. Routine hematoxyline and eosin (H&E) stain will be used for morphological analysis and for the determination of immune cell infiltrates. The samples will be assessed by the breast pathologist as previously described (65,66). One H&E slide and 20 unstained slides will be reserved for Gene Expression Profiling (described in section 9.2 below).
- 9.1.2 Immune cell infiltrates have previously been shown to correlate with both breast cancer-specific outcomes and response to neoadjuvant treatment (67). We anticipate that enhanced immune cell infiltration (determined as described above in 8.1.1, or with additional immunostains if needed and tissue available allows) will correlate with pathologic responses to RT.
- 9.1.3 Blood specimens (50mL, collected in 10mL lavender top EDTA tubes) will be obtained at the time of routine blood draws: once pre- and once post-radiation, (last day and up to one week after +/- 1 treatment) for future studies of immune markers/peripheral blood cells and other cancer and treatment related biomarkers that will attempt to predict radiation side effects and potentially treatment responses. These samples will be obtained at Froedtert Hospital, and in order to spare patient additional travel, those receiving radiation treatment outside Froedtert may opt out of the blood draw at the end of radiation. These samples will also be stored on the MCW Campus and analysis will be performed on campus. The process for handling specimens will be as follows:
 - 9.1.3.1 After collection, invert tube(s) multiple times to ensure adequate mixing of EDTA. ***Call the co-PI's laboratory ([name]) at [contact] to let them know they need to come pick up the PBMCs. If no answer, call the co-PI at [contact]. The plasma will be processed in the laboratory performing the blood draw, and the PBMCs will be collected by the PI's laboratory member for the remainder of the processing outlined below.**

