- 9.2.2 We will perform global gene expression profiling using RNAseq to identify differential expression patterns that correlate with response to radiation. We will utilize the MCW Human and Molecular Genetics Center Sequencing Core to perform RNAseq and analysis. Total RNA will be extracted using Trizol per the MCW Tissue Bank's standard procedure, and the total RNA will be poly-A purified, transcribed, and chemically fragmented using Illumina's TruSeq RNA library kit. Libraries will be prepared for each sample, indexed for multiplexing, and then sequenced on an Illumina HiSeq 2000. Briefly, we will plan to multiplex 4 libraries per lane x 8 lanes per flow cell, enabling us to test 32 samples per flowcell, a setup which has routinely yielded us 150-180 million reads (87.5% mapped reads) per lane. For data analysis, sequencing reads will be demultiplexed and compressed into FASTQ files using CASAVA 1.8 or equivalent software, aligned to the human genome by TopHat (69), and analyzed for transcript abundance using Cufflinks (70). Cufflinks produces FPKM (fragments per Kb of exon per million fragments mapped) values for all transcript isoforms. The CuffDiff2 program (part of Cufflinks package) then statistically analyzes differences in transcript abundance, taking into account variance between biological replicates and correction for false discovery rate (71).
- 9.2.3 Expression of genes from patients with pathologic complete response versus non-complete responders will be compared using an unpaired t test on all probes, with a false-discovery rate (FDR) of less than 0.05. If <15% complete pathologic responses are seen, then partial responses versus no response will be compared.
- 9.2.4 Expression of genes from patients with pre- and post-radiation will be compared, with a false-discovery rate (FDR) of less than 0.05.
- 9.2.5 Gene expression data from this patient group will be compared to previously published gene expression signatures for radiation sensitivity, and OncotypeDx, a metric that predicts chemotherapy response (79,89,90).
- 9.2.6 Correlation of MR parameters and gene expression differences will be performed as described previously (90). Correlation of MRI parameters and CT-imaging with pathologic responses will also be determined.

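### The interval from radiation to surgery can run from 5 to 8 weeks or more, and no response analysis accounts for it; this matters mainly for markers read on the surgical specimen

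*Combined protocol and SAP*

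**What the plan says.** Section 8.1 sets the timing of lumpectomy: it "will occur no sooner than 5 weeks following completion of RT, but should occur no later than 8 weeks". The lower limit is firm. The upper limit is a recommendation, so the span is at least 21 days and may be longer.

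Section 1.6 gives the reason for waiting. It contrasts this trial with an earlier single-fraction study ("surgery within 10 days of radiation versus at least 35 days after radiation") and appeals to rectal cancer: "In this disease site, waiting longer for surgery allows for improved tumor regression". Section 8.1 returns to the same source for the window as a whole: "In patients with rectal cancer, this interval has been shown to produce optimal response to pre-operative radiation".

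The analyses that use pathologic response are these:

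- **9.1.2**: immune cell infiltrate, assessed on stained tissue, is expected to show a relationship with response (it "will correlate with pathologic responses to RT").
- **9.2.3, repeated in 11.3**: expression in complete versus non-complete responders "will be compared using an unpaired t test on all probes, with a false-discovery rate (FDR) of less than 0.05". If fewer than 15% respond completely, partial responders are compared with non-responders instead. The specimen is not named. Section 9.2.1 provides RNA from both the biopsy and the surgical specimen.
- **9.2.6**: unspecified correlations of MR parameters with expression differences, and of imaging with pathologic response.
- **11.2**: the response rate with an exact confidence interval and a chi-square or Fisher test against historical controls.

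None of these adjusts for the interval, stratifies by it, or plans a sensitivity analysis on it.

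**The concern.** Two tumors of equal radiosensitivity could be classed differently because one was removed at week 5 and the other at week 8. How much this matters depends on when the marker was sampled.

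A marker from the pre-radiation biopsy cannot be changed by a later operating date. For it, the interval is extra noise in the outcome, unless scheduling is itself related to tumor biology.

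A marker from the surgical specimen is read at the same moment as the response. If both drift with time since radiation, they will be correlated across patients even when the marker has nothing to do with radiosensitivity. Immune infiltrate in the surgical specimen is in this position, and so is any post-radiation expression used in 9.2.3, 9.2.6 or 11.3.

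Objectives 2.2.7 and 2.2.8 seek imaging, expression and immune correlates of response, and 9.2.7 carries selected genes forward into a new signature. A timing artifact could be carried forward with them.

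**Working it through.** **The plan's own figures.** The documents give no sizing figure for pathologic response. The only one is the two-stage design in 11.1 (17 then 22 patients; suspend at 5 or more complications; reject the null at 7 or fewer of 39). Exact binomial calculation gives early stopping 0.6453 (stated 0.6453), type I error 0.047 (stated about 0.05) and power 0.805 (stated 0.80). It reproduces, and nothing below changes it. It supplies n = 39.

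**Step 1. How strongly could the interval relate to response?** The documents give no figure, so these are assumptions: residual tumor burden halves every 14 to 42 days, the between-tumor SD is 0.5 to 1.5 on the log10 scale, and intervals are spread evenly over days 35 to 56.

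- Shift over 21 days = 21 × log10(2) / half-life: 0.4515 at 14 days, 0.1505 at 42 days.
- Variance due to interval = shift² / 12: 0.0170 and 0.0019.
- Share of variance = that / (that + SD²).
 - Largest case: 0.0170 / (0.0170 + 0.25) = 6.4%, a correlation of √0.064 = 0.25.
 - Smallest case: 0.0019 / (0.0019 + 2.25) = 0.08%, a correlation of 0.03.

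**Step 2. Surgical-specimen marker with no true link to response.** If the interval correlates a with response and b with the marker, and nothing else links them, marker and response correlate a × b. With Fisher's z and n = 39, the two-sided 5% test rejects with probability P(Z > 1.96 − 6·atanh(ab)) + P(Z < −1.96 − 6·atanh(ab)), since √(39 − 3) = 6. Simulation used 40,000 replicates; the adjusted test is the partial correlation given interval.

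| a (response) | b (marker) | a × b | Formula | Simulated | Adjusted |
|---|---|---|---|---|---|
| 0.03 | 0.50 | 0.015 | 5.1% | 5.1% | 5.0% |
| 0.10 | 0.10 | 0.010 | 5.0% | 5.1% | 5.0% |
| 0.25 | 0.25 | 0.0625 | 6.6% | 6.7% | 5.0% |
| 0.25 | 0.50 | 0.125 | 11.7% | 11.8% | 5.1% |

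**Step 3. The responder t test itself.** A separate simulation (5,000 trials per setting, n = 39, average complete response 30%, intervals uniform on 5 to 8 weeks) varied the odds ratio of response per week from 1 to 2.

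- *Surgical-specimen marker, no true effect.* The largest unadjusted rejection rate was 6.4% with a drift of 0.25 SD per week (false mean difference up to 0.13 SD) and 8.8% with 0.5 SD per week (up to 0.24 SD). With the interval in a linear model, rejection was 4.5% to 5.6%.
- *Biopsy gene, no true effect.* Rejection was 4.7% to 5.5%, so no bias.
- *Biopsy gene with a true odds ratio of 2 per SD.* The mean difference fell from 0.63 to 0.60 SD and power from 0.44 to 0.39 at worst. Adjustment gave power 0.42 in that worst case.

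**The case against.** The strongest reply is that the protocol never says timing matters within the window. That is correct. The regression statement in 1.6 concerns rectal cancer and supports waiting at least 35 days rather than operating within 10. Section 8.1 then treats 5 to 8 weeks as a single favorable interval. A reader might infer that the protocol itself names the interval as a cause of response in these patients, and it does not. What remains is that the protocol borrows the rectal-cancer reasoning to choose the interval and offers no evidence that regression is flat from week 5 to week 8.

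A second reply is that the main responder comparison may be immune. Section 9.1.1 stores whatever tumor remains after radiation, and a complete responder should have essentially none. The complete versus non-complete contrast would then in practice rest on biopsy tissue, where there is no bias. This largely stands. It leaves immune infiltrate, the fallback contrast of partial versus no response, and any use of post-radiation expression in 9.2.6. Because 9.2.3 does not name the specimen, the reader cannot be sure.

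Third, Ki-67 might be taken as another confounded marker. Section 9.1.6 uses it as a measure of response, and no analysis relating it to pathologic response is planned, so it does not belong here.

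Fourth, these analyses generate hypotheses, and 9.2.7 defers validation to future studies. That stands and limits the weight of the point.

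**Conclusion.** The concern holds in a limited form. The interval varies by three weeks or more, the response analyses ignore it, and for markers read on the surgical specimen this could create a modest false association: about 5% to 12% rejection at a nominal 5% level. For biopsy markers the cost is noise and a small loss of power.

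The size rests on assumed regression rates and tumor-to-tumor spread, on an even spread of intervals over days 35 to 56, and on a marker-interval correlation of up to 0.5. Operations after week 8 would widen the spread and raise the ceiling of 0.25. If regression is flat across the window, there is no bias.

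A reader might infer much larger error rates. Correlations of 0.4 or 0.5 on both sides would give about 16% or 34%, but those values for response exceed the 0.25 that the regression assumptions allow, so they should not be used.

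Nor does the point bear on the primary complication endpoint or argue for a different surgical window. The count of complete responses that triggers the 15% switch in 9.2.3 might itself depend on timing, but a covariate would not alter that, so the switch is no part of the case. The point merits consideration; it is not a required correction.

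**What to change.** - In 9.1.2, 9.2.3, 9.2.6 and 11.3, state which specimen each marker comes from.
- For surgical-specimen markers related to pathologic response, replace the unadjusted test with a linear or partial-correlation model that includes days from last fraction to surgery. For 9.2.3 this is a linear model of expression on response group and interval, with the same false-discovery threshold. Without the interval term it is the planned t test (in its equal-variance form).
- For biopsy markers, keep the planned test and add the interval model as a sensitivity analysis.
- In 11.2, report the distribution of the interval alongside the response rate.

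Both dates are already needed to check compliance with 8.1, so no new data are collected. The cost is one degree of freedom in about 39 patients, plus a sentence saying how the adjusted model sits beside the CuffDiff2 analysis, for which 9.2.2 and 11.3 describe no covariate.

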8.2 Sentinel lymph node biopsy and management of the axilla

Sentinel lymph node biopsy should be performed at the time of lumpectomy. But at the discretion of the treating physicians, it may be performed prior to the initiation of radiation therapy. Dual tracer with radiocolloid together with blue dye is required. If a sentinel lymph node is positive for metastatic disease with any focus >0.2 mm (i.e. stage N1mic or higher), axillary node dissection may be performed at the discretion of the treating physicians. In the unlikely event that there are 4 or more positive lymph nodes, patients will require RT to the regional lymph nodes. Given the patient selection criteria and pre-treatment evaluation, this scenario would be extremely unlikely.

8.3 Management of a positive margin

The need for surgical re-excision after the initial lumpectomy because of close or positive margins will be determined by the treating surgeon and radiation oncologist. For any patient with a positive margin, re-excision is required unless technically not possible (i.e. poor anesthesia risk for the patient, inability to resect additional breast tissue at the site of the positive margin).

8.4 Post-operative Radiation Therapy

It is conceivable that patients deemed appropriate for APBI and are study eligible may have findings on final pathology that would make them inappropriate candidates for APBI. Careful selection criteria for this study make this scenario very unlikely. However, if a patient has a nodal metastasis >2 mm (N1 or higher), post-operative whole breast irradiation should be strongly considered. Similarly, whole breast irradiation should also be considered for patients with persistently positive resection margins and then refuse mastectomy or with an extensive intraductal component. Regional nodal irradiation will be added to the whole breast irradiation and required for patients with 4 or more positive nodes, and should be considered for those with 1-3 positive nodes. Dose and fractionation of the subsequent treatment will be left to the discretion of the treating radiation oncologist. A boost to the surgical bed in the breast should be discouraged.

This approach is patterned after that used on the TARGIT-A trial. In that study, intra-operative APBI was administered to patients before the final results of surgical pathology were available. Patients who were found to have high risk features and not deemed appropriate for APBI alone after final pathology received whole breast irradiation without significant adverse effect (96).

9.0 Pathologic Evaluation and Genetic Evaluation of Tissue Specimens

9.1 Pathological Evaluation and Immune Biomarkers

- 9.1.1 The surgical specimens will be subject to routine pathological analysis. Remaining tissue from the pre-treatment biopsy, as well as any residual tumor tissue post-RT, will be stored in accordance with MCW department of Pathology guidelines. Routine hematoxyline and eosin (H&E) stain will be used for morphological analysis and for the determination of immune cell infiltrates. The samples will be assessed by the breast pathologist as previously described (65,66). One H&E slide and 20 unstained slides will be reserved for Gene Expression Profiling (described in section 9.2 below).
- 9.1.2 Immune cell infiltrates have previously been shown to correlate with both breast cancer-specific outcomes and response to neoadjuvant treatment (67). We anticipate that enhanced immune cell infiltration (determined as described above in 8.1.1, or with additional immunostains if needed and tissue available allows) will correlate with pathologic responses to RT.
- 9.1.3 Blood specimens (50mL, collected in 10mL lavender top EDTA tubes) will be obtained at the time of routine blood draws: once pre- and once post-radiation, (last day and up to one week after +/- 1 treatment) for future studies of immune markers/peripheral blood cells and other cancer and treatment related biomarkers that will attempt to predict radiation side effects and potentially treatment responses. These samples will be obtained at Froedtert Hospital, and in order to spare patient additional travel, those receiving radiation treatment outside Froedtert may opt out of the blood draw at the end of radiation. These samples will also be stored on the MCW Campus and analysis will be performed on campus. The process for handling specimens will be as follows:
 - 9.1.3.1 After collection, invert tube(s) multiple times to ensure adequate mixing of EDTA. ***Call the co-PI's laboratory ([name]) at [contact] to let them know they need to come pick up the PBMCs. If no answer, call the co-PI at [contact]. The plasma will be processed in the laboratory performing the blood draw, and the PBMCs will be collected by the PI's laboratory member for the remainder of the processing outlined below.**
 - 9.1.3.2 **Performed by the blood draw laboratory:** Centrifuge specimen(s) within one hour of collection in a standard clinical centrifuge at ~2500 RPM for 10 minutes at 4°C (preferred). If unable to process the samples at 4°C then spinning at room temperature is acceptable if done within 2 hours of draw. If the interval between specimen collection and processing is anticipated to be more than one hour, keep specimen on ice until centrifuging is performed.
 - 9.1.3.3 **Performed by the blood draw laboratory:** Carefully pipette and aliquot 0.5mL plasma into 8 cryovials labeled with case numbers, collection date/time, time point collected and clearly mark specimen as "plasma". Avoid pipetting up the buffy coat layer.
 - 9.1.3.4 Place cryovials into biohazard bag and immediately freeze at -70 to -90°C.
 - 9.1.3.5 Store frozen plasma until ready for analysis
 - 9.1.3.6 **Performed by the PI's laboratory:** PBMCs should be separated using sterile and endotoxin free Ficoll density gradient solution. The peripheral blood mononuclear cells (PBMCs) should be removed and pooled. The PBMC layer should be resuspended

in three times the volume of cold sterile PBS. Cells should be counted using a hemocytometer and the total cell number should be noted. The expected yield is 1-2 million cells per ml of blood.

9.1.3.7 **Performed by the PI's laboratory:** The PBMCs collected from 3 lavender top tubes will be divided into three aliquots. Roughly two-thirds of the cells should be cryopreserved for future analysis (see next item). Roughly one-third of the cells will be placed in RNAlater (see instructions below) and snap frozen with liquid nitrogen and stored at -70 to -80°C for future RNA extraction. If there are more than 15E6 viable cells the RNA later aliquot should be limited to a total of 5E6 cells and the additional cells should be cryopreserved at -70 to -90 °C, thus deviating from the 2:1 aliquoting.

9.1.3.8 **Performed by the PI's laboratory:** Cryopreservation; After counting, PBS washed PBMCs should be divided into aliquots of 5 million cells and spun down at approximately 1,000-1,500 rpm (400 x g) for 10 minutes. Each aliquot should be resuspended in 1ml of cold sterile CryoStor CS10 freeze media (catalog number 07930, STEMCELL technologies) which contains 10% DMSO. Each 1ml aliquot should be placed in a cryopreservation tube and the lid should be tightly secured. Tubes should be placed into a "[name]" or other slow freeze container and placed into a -70 to -80°C freezer for 12-24 hours. Tubes should then be transferred to and stored in vapor phase liquid nitrogen (-135°C) until analyzed in batches.

9.1.3.9 **Performed by the PI's laboratory:** RNA later: After counting, PBS washed PBMCs should be spun down at approximately 1,000-1,500 rpm (400 x g) for 10 minutes. The cell pellet should be re-suspended in 1ml of RNAlater solution snap frozen in liquid nitrogen and stored at -70 to -80°C until analyzed in a batched manner.

